## 7.1. Discontinuation of Study Intervention

When necessary, a participant may be permanently discontinued from study intervention. If so, the participant will remain in the study and follow procedures for remaining study visits, as shown in the SoA.

Participants who stop the study intervention permanently may receive another glucose-lowering medication. The new glucose-lowering medication will be recorded on the CRF for antihyperglycemic medications.

A participant should be permanently discontinued from study intervention if

- the participant becomes pregnant during the study
- the participant requests to discontinue study intervention
- the participant is receiving a 100 U dose and needs a dose reduction
- the participant is diagnosed with an active or untreated malignancy, except for successfully treated basal or squamous cell carcinoma
- the participant did not take insulin glargine for more than 21 consecutive days or missed more than 3 consecutive doses of LY3209590 at any time during the study, or
- in the opinion of the investigator, the participant should permanently discontinue the study intervention for safety reasons.

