# Hypoglycemia analysis

The analysis periods of 0-16, 0-26, 0-52, 16-26, and 26-52 weeks of treatment will be considered.

The participant-reported hypoglycemia will be analyzed using data from the e-diary by

- Level 1 (glucose  $\geq$ 54 to <70 mg/dL)
- Level 2 (glucose <54 mg/dL)
- Level 3 (severe), and
- the composite of Levels 2 and 3.

This table gives definitions for documented hypoglycemia events.

Documented hypoglycemia	Definition
All documented hypoglycemia	episodes for the 24-hour period
Non-nocturnal hypoglycemia	episodes during 0600 hours to midnight
Nocturnal hypoglycemia	episodes during midnight to 0600 hours

The incidence and rate of hypoglycemia will be summarized by treatment and analysis period for different types of hypoglycemia.

For continuous safety variables, such as laboratory measures, vital signs and weight, MMRM or ANCOVA models will be used.

For categorical safety variables, such as AEs, incidence of hypoglycemia, and treatmentemergent abnormal laboratory measurements, either Fisher's exact test or logistic regression will be used for treatment comparison.

Further details for assessing all safety measures will be provided in the SAP.

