# 3. Analysis Sets

This table defines the populations for the purpose of analysis.

Analysis Populations or Datasets	Description	
Entered Population	All participants who sign the informed consent form.	
Randomized Population	All randomized participants. Participants will be analyzed according to the treatment they were assigned.	
Modified Intent-to-Treat (mITT) Population	All randomized participants who took at least 1 dose of study treatment. Participants will be analyzed according to the treatment they were assigned.	
Efficacy Analysis Set 1 (EAS1) for treatment regimen estimand on efficacy measures	The data will include:  • mITT Population excluding participants discontinuing the study treatment due to inadvertent enrollment, and  • all measurements regardless of the use of study treatment or rescue medications.	
Efficacy Analysis Set 2 (EAS2) for efficacy estimand on efficacy measures	The data will include:  • mITT Population excluding participants discontinuing the study treatment due to inadvertent enrollment, and  • measurements up to the early discontinuation of study treatment or the initiation of rescue medication.  • the data cutoff for participants who had intercurrent events is defined by the earliest date from below dates for individual participants except for the analysis on study dose:  • the date of last study dose + 10 days for LY3209590, or +1 day for glargine  • the start date of the first rescue medication  • the data cutoff for analysis on study dose is defined by the earliest date from below dates for individual participants:  • the date of last study dose  • the start date of the first rescue medication	
Safety Analysis Set (SS)	The data will include:         • mITT Population, and         • all measurements regardless of the use of study treatment or rescue medications.	

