# 4. Statistical Analyses

#### 4.1. General Considerations

Statistical analysis of this study will be the responsibility of Eli Lilly and Company (Lilly) or its designees. Any change to the data analysis methods described in the protocol will require an amendment ONLY if it changes a principal feature of the protocol. Any other changes to the data analysis methods described in the protocol, and the justification for making the change, will be described in the SAP or the final clinical study report. Additional exploratory analyses of data will be conducted as deemed appropriate.

Unless otherwise stated, the efficacy analyses will be conducted on either EAS1 or EAS2. Primary and key secondary (gated) objectives will be based on both treatment regimen estimand and efficacy estimand, while the other secondary and tertiary efficacy measures will be based on efficacy estimand. For treatment regimen estimand, EAS1 (see the definition in Section 3) will be used for analysis. For efficacy estimand, other secondary and tertiary efficacy measures, EAS2 (see the definition in Section 3) will be used for analysis.

Unless otherwise noted, the safety analyses will be conducted on the SS. Percentages will be calculated using the mITT population as the denominator. For events that are sex-specific, the denominator and computation of the percentage will include only participants from the given sex.

All tests of treatment effects will be conducted at a 2-sided alpha level of 0.05 and 2-sided 95% CIs will be calculated.

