Fasting serum glucose	The baseline is the last non-missing	All scheduled visits after the day of
	assessment prior to or on the day of	first dose up to Visit 33 (Week 52) in
	the first dose of study treatment.	EAS2 for MMRM (efficacy
		estimand)
		Planned measurements at scheduled
		visits will be included.
		Data at Visit 33 (Week 52) and Visit
		25 (Week 26) in EAS1 for
		ANCOVA with multiple imputation
		for missing data (treatment regimen
		estimand)
		For sensitivity analysis to compare
		the treatment effect of LY3209590
		with autoinjector and insulin
		glargine:
		• LY3209590: after the day of first
		dose of study treatment up to the
		visit prior to or at the time of
		switch to prefilled pen in EAS2
		for MMRM (efficacy estimand).
		• Glargine: after the day of first
		dose of study treatment up to
		Visit 33 (Week 52) in EAS2 for
		MMRM (efficacy estimand).
Insulin dose during the treatment	N/A	All scheduled visits between Visit 3
period period	17/11	and Visit 33 in EAS2 for MMRM.
		The averages of weekly basal insulin
		doses between visits for individual
		participants will be used in the
		•
		analysis. (Section 4.4.2.1)

Analysis	Baseline Observations	Postbaseline Observations
Participant-reported	The baseline period is the lead-in	Treatment period starts at or
hypoglycemia	period prior to the first dose date of	after the first dose date of study
	study treatment.	treatment and ends
		o At Visit 33 (Week 52) if
		completed treatment
		
 
on the last dose date of
 

		study treatment + 10 days
		for LY3209590, +1 day for
		glargine if discontinued
		study treatment early
		Post-treatment period starts from
		o Visit 33 (Week 52) +1 day
		if completed treatment
		
 
last dose date of treatment
 

		+11 days for LY3209590,
		+2 days for glargine if
		discontinued study
		treatment early and ends on
		the last date in the study
TEAEs	The baseline period includes the	Safety analysis period starts after the
	screening/lead-in period up to the	first dose and ends at the last visit in
	first dose of study treatment (CRF is	the study including safety follow-up
	used to determine).	period.
Safety laboratory tests, vital signs,	The baseline will be the last non-	All scheduled visits after the first
and body weight	missing assessment prior to or on	dose date up to Visit 802 for
	the first dose date of study	MMRM or ANCOVA
	treatment.	
		Planned measurements at

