		Appendix 8 [Section 6.8] for
		details) will be used for treatment
		comparison.
		The plots of the mean cumulative
		functions (MCFs) by each treatment
		arm will also be created. The
		population mean for cumulative
		number of events up to time $t$ , $M(t)$ ,
		will be estimated using a
		nonparametric estimation method
		described by Nelson (2003).
Incidence of Level 1	Baseline, 0-16, 0-26, 0-52, 16-26,	Logistic regression with treatment
hypoglycemia events:	26-52 weeks, post-treatment period	and baseline HbA1c as covariates.
All documented		
Incidence of Level 2	Baseline, 0-16, 0-26, 0-52, 16-26,	Logistic regression with treatment
hypoglycemia events:	26-52 weeks, post-treatment period	and baseline HbA1c as covariates.
All documented		
Incidence of Level 3	Baseline, 0-26, 0-52, 26-52 weeks,	Logistic regression with treatment
hypoglycemia events:	post-treatment period	and baseline HbA1c as covariates.
All documented		
Incidence of Level 2/3	Baseline, 0-16, 0-26, 0-52, 16-26,	Logistic regression with treatment
hypoglycemia events:	26-52 weeks, post-treatment period	and baseline HbA1c as covariates.
All documented		
Nocturnal		
Non-nocturnal		

Endpoint	Analysis Period*	Statistical Method
Potential persistent-recurrent	Safety analysis period (see	The number of participants with at
hypoglycemia events	definition in Section 4.6)	least one event will be summarized

 
identified by
 
		and compared by Fisher's exact test.
investigator		The number of events will also be

 
identified by pre-
 
		provided.
criteria (defined in		
Appendix 9		
[Section 6.9])		

Abbreviations: HbA1c = hemoglobin A1c; Level 2/3= Level 2 and Level 3 composite; mITT = modified Intent-to-Treat.

Note: The hypoglycemia yearly rate during defined period is calculated by the number of hypoglycemia within the period/number of days patient at risk within the period times 365.25. For rare events, 100-year rate will be provided. The hypoglycemia incidence during defined period indicates if the patient has at least 1 hypoglycemia events within the period (Yes/No).

A sensitivity analysis will be done for selected hypoglycemic endpoints where all hypoglycemic events are considered one hypoglycemic event until a subsequent glucose value is  $\geq 70 \text{ mg/dL}$ .

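### Hypoglycemia percentages for Weeks 16-26 and 26-52 keep participants with no day at risk in the denominator and are modestly understated

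*SAP*

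**What the plan says.** **Denominator.** SAP 4.1, on safety analyses: "Percentages will be calculated using the mITT population as the denominator". SAP 4.6, which contains the hypoglycemia analyses, repeats the rule. The only exception given with it is for sex-specific events. SAP 3 defines the mITT population as "All randomized participants who took at least 1 dose of study treatment", so its size is fixed at first dose.

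**Windows.** Protocol 9.3.5: "The analysis periods of 0-16, 0-26, 0-52, 16-26, and 26-52 weeks of treatment will be considered". SAP 4.6.3.1 adds a baseline and a post-treatment period. Level 3 events have no 16-26 window.

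**Incidence and rate.** The note under the SAP 4.6.3.1 table defines incidence without an at-risk condition: "The hypoglycemia incidence during defined period indicates if the patient has at least 1 hypoglycemia events within the period (Yes/No"). The same note divides the rate by the "number of days patient at risk within the period times 365.25". The incidence method is given as "Logistic regression with treatment" and baseline HbA1c as covariates. The participants entering each window's model are not stated.

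**End of the treatment period.** In the SAP 4.1 table, the hypoglycemia treatment period of an early discontinuer on LY3209590 ends at the last dose date of "study treatment + 10 days"; for glargine it is last dose plus 1 day. Later time belongs to the post-treatment period.

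**Arm-specific exit.** Protocol 7.1 lists, as a ground for permanent discontinuation of study intervention, that "the participant is receiving a 100 U dose and needs a dose reduction". Protocol 6.5.2.3 provides a dose reduction for glargine participants who meet the corresponding hypoglycemia criteria.

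**The concern.** Someone who stops treatment at Week 8 has no treatment-period day in Weeks 16-26 or 26-52 and cannot have an event counted there. Under the written rule that person still sits in the denominator as event-free. The percentage falls below the incidence among those who could have had an event, and it describes a different group from the rate printed beside it. A participant with zero exposure has no defined log-exposure offset, so the rate model cannot include them.

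The comparison between arms is also exposed. The 100 U rule takes some LY3209590 participants off treatment because of hypoglycemia, and the glargine schedule has no counterpart. If the two arms lose different shares before a window opens, the denominators alone create a difference in incidence.

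**Working it through.** **Inputs.** 670 randomized 1:1, so 335 per arm (SAP 5). Dropout 15% at Week 52 (SAP 5). Windows opening at Week 16 and Week 26 (SAP 4.6.3.1). The documents give no hypoglycemia incidence and no discontinuation by arm or over time. Those values are assumed below, and mITT is taken as 335 per arm.

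**The plan's own figure.** 335 × (1 − 0.15) = 284.75, which agrees with the stated 284 per arm completing 52 weeks of treatment.

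**Share with no day in the window**, if the 15% describes leaving treatment and accrues linearly:
- Before Week 16: 0.15 × 16/52 = 4.6%, leaving about 319 of 335 per arm at risk.
- Before Week 26: 0.15 × 26/52 = 7.5%, leaving about 310 of 335.
- A constant hazard gives nearly the same: 1 − 0.85^(16/52) = 4.9% and 1 − 0.85^(26/52) = 7.8%.
- Ceiling: all 15% leave before the window opens.

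**Dilution.** Reported incidence = incidence among those at risk × (1 − share with no day in the window).

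| At-risk incidence | Weeks 16-26 (4.6% out) | Weeks 26-52 (7.5% out) | Ceiling (15% out) |
|---|---|---|---|
| 5% | 4.8% | 4.6% | 4.25% |
| 10% | 9.5% | 9.25% | 8.5% |
| 20% | 19.1% | 18.5% | 17.0% |

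**Effect on the comparison.** With equal shares out, the factor (1 − share) cancels and the ratio of incidences is unchanged. With a 5-point gap, assuming 10% out on LY3209590, 5% out on glargine and 10% true risk in both arms:
- Reported incidence: 0.10 × 0.90 = 9.0% against 0.10 × 0.95 = 9.5%.
- Odds ratio: (0.090/0.910) / (0.095/0.905) = 0.94.
- Risk difference: −0.5 percentage points, from the denominators alone.

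**Windows opening at Week 0.** Every mITT participant has taken a dose and starts at risk, so Weeks 0-16, 0-26 and 0-52 do not have this problem.

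**The case against.** **A fixed denominator keeps the groups as randomized and treated.** Restricting to those still at risk conditions on a post-randomization event. It also removes the same hypoglycemia-prone LY3209590 participants, so a depleted arm is still compared with a less depleted one. This stands as a limit on the fix. It does not rescue the mITT denominator: stoppers' later events are already outside the treatment period, so the fixed denominator hides the attrition without restoring what was lost.

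**The safety set keeps all measurements, so stoppers might still contribute events.** SAP 4.1 sets a specific end to the hypoglycemia treatment period, and Protocol 9.3.5 describes the windows as weeks of treatment. Events after that end belong to the post-treatment period.

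**The denominator rule concerns percentages.** A reader might infer that the SAP also puts all mITT participants into each window's logistic regression. It does not say so. For the model, the analysis set is unstated.

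**Post-treatment period.** A reader might extend the claim of understatement here. The documents do not support it. Participants who stop treatment stay in the study (Protocol 7.1), so early stoppers can have months of post-treatment time against about 5 weeks for completers. Unequal follow-up is the larger issue, and its net direction is not known.

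**Size.** A reader might take the arm gap to be large: 15% against 5% out at 10% true risk would give an odds ratio of 0.89. Nothing in the documents supports that split. Protocol 4.3 reports simulated drop-out due to hypoglycemia below 5% at the 100 U starting dose. The 100 U rule is also not automatic: Protocol 7.1 says should, and 6.5.1.3 has the investigator first rule out other contributing factors.

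**Conclusion.** The point holds for the percentages in Weeks 16-26 and 26-52, at low severity. Following the SAP as written understates them by about 5% and 7.5% relative under linear accrual of the 15% dropout, and by at most 15% if actual discontinuation stays within that figure. The comparison between arms moves only if the shares not at risk differ. The 100 U rule makes that possible, but the documents give no size for it, and the odds ratio of 0.94 is an illustration of an assumed 5-point gap.

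The affected results are supportive interval summaries outside the gatekeeping procedure. The primary and gated HbA1c analyses, the 0-52 week hypoglycemia secondary endpoints and the event rates in every window are untouched.

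**What to change.** Add to SAP 4.6.3.1:
- For Weeks 16-26 and 26-52, percentages and logistic regression include safety-set participants with at least one treatment-period day at risk in the window, and that number is shown per arm.
- These comparisons are conditional on remaining on treatment and do not remove selection from earlier discontinuation.
- Windows starting at Week 0 keep the mITT denominator.
- For the post-treatment period, show the number at risk and the follow-up time per arm, and base interpretation on the exposure-adjusted rate.

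The cost is a short SAP insertion and an at-risk flag that the rate offset already requires. Later-window percentages become slightly higher and are no longer on the full mITT set. The rule does not adjust for participants who leave partway through a window; the rate does.

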#### Study participants treated with LY3209590

Since LY3209590 has a half-life of approximately 17 days, a careful titration of any new antihyperglycemic treatment will be necessary to prevent hypoglycemia due to overlapping action. The investigator should consider titrating the daily insulin to reach 50% of the required daily dose at approximately 2 weeks and 80% at approximately 4 weeks.

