# 9.3.3.2. Other Secondary Endpoints

Other secondary endpoints include various measures for efficacy, safety, and patient-reported outcome questionnaires.

Unless otherwise stated, efficacy measures and patient-reported questionnaires will be analyzed using the EAS2.

Safety measures will be analyzed using the SS regardless of treatment discontinuation and use of rescue medications.

Analysis details will be provided in the SAP.

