### 4.6.1. Extent of Exposure

Duration of exposure to study treatment will be summarized. No p-values will be reported in these tables as they are intended to describe the study populations, rather than test hypotheses about them. Total patient-years of exposure will be reported. The number and proportion of participants falling into the following different exposure categories will also be summarized by study treatment

- $>0, \ge 30 \text{ days}, \ge 90 \text{ days}, \ge 180 \text{ days}, \ge 365 \text{ days}$
- >0 and <30 days, ≥30 and <90 days, ≥90 and <180 days, ≥180 and <365 days

Exposure on study treatment will be calculated as

- LY3209590: date of the last treatment administration date of first treatment administration + 7 days
- Insulin glargine: date of the last treatment administration date of first treatment administration + 1 day

Total patient-years of exposure will be calculated by the sum of duration of exposure in days divided by 365.25. The following summary statistics will be provided: n, mean, standard deviation, median, minimum, maximum, interquartile range, and total exposure (that is, total patient-years).

All participants who complete the study treatment period are required to complete a safety follow-up period and participants who discontinue the study treatment prematurely are encouraged to remain in the study for safety monitoring. The duration on study from the first dose of study treatment to the final study disposition date will also be summarized by treatment.

A listing of exposure to study treatment will be provided.

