## 4.9. Changes to Protocol-Planned Analyses

There are no changes but additional details are provided to the analyses described in the protocol.

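### For participants who stop treatment early, the SAP ends the Weeks 0-52 hypoglycemia window at last dose +10 days (LY3209590) or +1 day (glargine), an undeclared narrowing of the protocol's rule for safety measures

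*SAP*

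**What the plan says.** The SAP 4.1 table sets the hypoglycemia treatment period by treatment status:

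- Completers, both arms: it ends "At Visit 33 (Week 52) if" treatment was completed.
- Early discontinuers: it ends at the last dose date of "study treatment + 10 days" "for LY3209590, +1 day for" glargine. The row does not cut data at rescue.
- The post-treatment period for early discontinuers then starts at last dose plus "11 days for LY3209590" (plus 2 days for glargine) and runs to the last date in the study. SAP 4.6.3.1 lists it as its own analysis period, next to 0-52 weeks, for Level 1, 2, 3 and 2/3 rate and incidence.

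Protocol 9.3.3.2 says: "Safety measures will be analyzed using the SS regardless of treatment discontinuation and use of rescue medications". Protocol 9.2 and SAP 3 both define that set as holding all measurements. The only 10-day cutoff in the protocol's statistical section is in 9.3.1, and it applies to other secondary and tertiary efficacy measures on EAS2.

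In the same SAP 4.1 table, the adverse event row runs to the last study visit, and the laboratory, vital sign and weight rows run to Visit 802 or the last visit.

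On stopping, Protocol 6.9 says: "Since LY3209590 has a half-life of approximately 17 days". Protocol 7.1 keeps participants who stop treatment in the study on the remaining visit schedule, which records hypoglycemia at every visit.

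SAP 4.9 says: "There are no changes but additional details are provided to the analyses described in the protocol".

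**The concern.** Level 2/3 rate and incidence, overall and nocturnal, are the hypoglycemia comparisons among the secondary safety endpoints. Whether they describe the assigned strategy over 52 weeks or only time on drug plus a short tail is a choice of estimand. The protocol's general rule points to the first and the SAP row implements the second, without saying so.

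Two features make the choice matter here. First, the LY3209590 tail is short against the drug's own half-life. Second, stopping is not independent of the outcome. Under Protocol 6.5.1.3 and 7.1, a participant at 100 U who meets the hypoglycemia criteria for dose reduction is taken off study treatment. The glargine rules in Protocol 6.5.2.3 contain no such step. An investigator may stop treatment for safety in either arm, but a rule that turns hypoglycemia directly into discontinuation exists only for LY3209590.

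Incidence is exposed as well as rate. The planned logistic model contains treatment and baseline HbA1c but no time at risk, so a participant who stops early and is event-free in a short window counts as event-free for Weeks 0-52.

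**Working it through.** **The plan's own figure.** 670 randomized 1:1 gives 335 per arm. With 15% dropout, 335 × 0.85 = 284.75, which matches the stated 284 completers. No sample size or power is stated for hypoglycemia.

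**Drug remaining when the window closes.** Input: half-life about 17 days (Protocol 6.9). Assumption: simple exponential decline after the last dose, residual = 0.5^(t/17).

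- Day 10: 10/17 = 0.59 half-lives; 0.5^0.588 = 0.665, so about 67% of the level at the last dose remains. For half-lives of 14 to 20 days the range is 61% to 71%.
- Day 10 against the usual pre-dose level at day 7: 0.5^(3/17) = 0.885, about 88%.
- Day 35: 24%. Day 85 (five half-lives): 3%.

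**Person-time that leaves the Weeks 0-52 endpoint.** The documents give no share for treatment discontinuation. I use 15%, borrowed from the dropout figure, with a range of 5% to 20%. I also assume that stopping is uniform over 364 days and that everyone who stops stays in follow-up.

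- LY3209590: mean days lost per discontinuer = 354²/(2 × 364) = 172.1. Share = 0.15 × 172.1/364 = 7.1%, or about 24 person-years (50.25 × 172.1/365.25 = 23.7).
- Glargine: 363²/(2 × 364) = 181.0 days. Share = 0.15 × 181.0/364 = 7.5%, or about 25 person-years.
- For 5% to 20% stopping, the shares are 2.4% to 9.5% (LY3209590) and 2.5% to 9.9% (glargine).

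**Part of that time with LY3209590 still present (day 11 to day 85).**

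- Upper bound, with every discontinuer contributing all 75 days before Week 52: 0.15 × 75/364 = 3.1%.
- Under uniform timing: (75 × 279 + 75²/2)/364 = 65.2 days each, so 0.15 × 65.2/364 = 2.7%, about 9 person-years.

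**What this could do to the LY3209590 rate.** Take the counted person-time as 1, add 0.031, and let k be the event rate in the added time relative to the counted rate. The combined rate changes by (1 + 0.031k)/1.031:

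- k = 0.5: 0.985
- k = 1: 1.000
- k = 2: 1.030
- k = 4: 1.090

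The documents give no value for k, so even the sign is open.

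**The case against.** The best defence is that the endpoint itself is worded as events in the treatment period (Protocol 3), that Protocol 9.3.5 expresses the hypoglycemia analysis periods in weeks on treatment, and that the protocol leaves the details to the SAP. On that reading the SAP has only filled in a definition. This has some force, and it is why I call the point an unreconciled narrowing and not a flat contradiction. It does not settle the matter. The protocol describes the treatment period as 52 weeks, never as ending shortly after the last dose, and 9.3.3.2 is explicit about discontinuation.

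A reader might infer three stronger things that the documents do not support.

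- *That events are dropped in one arm.* They are not. They move to a defined post-treatment period with planned rate and incidence analyses, both arms are cut, and completers are counted to Visit 33. Severe events are also serious adverse events collected through follow-up, persistent-recurrent hypoglycemia is assessed to the end of the study, and the HbA1c/hypoglycemia composites treat anyone discontinuing before Week 52 as having had the event. However, the post-treatment table pools completers' follow-up with discontinuers' time of very different length, so it cannot give a Weeks 0-52 estimate regardless of discontinuation.
- *That the window favours LY3209590.* This needs k above 1. Drug level falls once dosing stops, the warning in Protocol 6.9 concerns overlap with a new treatment, and later events may reflect replacement therapy. The event that triggers stopping at 100 U normally falls before the cutoff and is counted.
- *That the rate denominator is materially wrong.* SAP 4.6.1 adds 7 days to LY3209590 exposure ("date of first treatment administration + 7 days") while events count to day 10. The effect is about 0.15 × 3/364 = 0.12%, and the note under the 4.6.3.1 table already uses days at risk within the period.

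**Conclusion.** The point holds as an undeclared narrowing that should be corrected. For early discontinuers, the SAP replaces the protocol's rule for safety measures with an on-treatment window whose LY3209590 tail closes with about two thirds of the drug level remaining, in an arm where hypoglycemia can itself force discontinuation.

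Up to about 7% of person-time per arm is affected, of which at most about 3% of LY3209590 person-time is drug-active. Both figures rest on 15% stopping early and all remaining in follow-up. Anyone who leaves the study contributes nothing later, so the figures are upper bounds for that share. Direction and size of bias are unknown.

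The Weeks 0-52 period is read here as limited by the SAP 4.1 treatment period, because the post-treatment period is listed separately. The asterisk on the analysis-period column in 4.6.3.1 has no visible footnote in the text reviewed. The affected endpoints are outside the gated testing, so the HbA1c conclusions do not depend on this. What depends on it is whether the trial can report the hypoglycemia comparison that the protocol describes.

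**What to change.** 1. In SAP 4.1 and 4.6.3.1, add a Weeks 0-52 analysis of Level 2/3 rate and incidence, all documented and nocturnal, on the Safety Analysis Set. Count every event to Week 52 regardless of treatment discontinuation, and use days at risk in that same window as the offset in both arms.
2. Keep the on-treatment analysis beside it, labelled as such.
3. Reconcile Protocol 9.3.3.2 with the hypoglycemia row of SAP 4.1, and declare any remaining difference in SAP 4.9.

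The cost is SAP wording and one extra run of models already planned, on data already collected. The drawback is that some counted events will occur on replacement glucose-lowering therapy. Showing the two analyses side by side lets a reader see how much that matters.
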